7.2.2 DINAMO Mono

It is not planned to test specific hypotheses because of the exploratory nature of DINAMO™ Mono.

7.3 PLANNED ANALYSES

The statistical analysis will be based on the following populations.

Treated set

The treated set (TS) will include all patients who are treated with at least one dose of randomised study medication. The TS is the basis for safety analyses.

Modified intention-to-treat set

The modified intention-to-treat set (mITT) will include all randomised patients who are treated with at least one dose of study medication and have a baseline HbA1c measurement. The mITT is the basis for the primary analyses.

Per protocol set

The per protocol set (PPS) will include all patients in the mITT set who do not have any important protocol deviations (IPD) which can be expected to have a distorting influence on the assessment of the primary endpoint. Details regarding the definitions of IPDs will be provided in the Trial Statistical Analysis Plan (TSAP) and the decision to exclude patients from the PPS will be made prior to database lock.

The term “baseline” refers to the following definitions according to the individual analysis period.

- *Study baseline*: Last observed measurement prior to administration of any initially randomised study medication at Day 1.
- *Titration baseline*: Last observed measurement prior to administration of the re-randomised study medication for the initial empagliflozin patients at Week 14.
- *Safety baseline*: Last observed measurement prior to administration of the re-randomised study medication for the initial placebo patients at Week 26.

For analyses up to Week 26, data collected after the first intake of study medication in the extension period will be censored.

Analyses up to Week 12 and Week 52 will be considered exploratory in nature. The study is not powered to compare empagliflozin with linagliptin at Week 12, Week 26 and Week 52, or to compare empagliflozin 10 mg with empagliflozin 25 mg at Week 52. No hypothesis testing is planned, and only descriptive statistics will be provided.

The anticipation for the patients who would have taken the wrong study medication is low. Therefore all analyses will be based on the randomised treatments. All patients with wrong study medication will be listed.

For HbA1c analyses, both NGSP certified and non-NGSP certified HbA1c values will be used in HbA1c endpoints analyses, given that they are in the same unit. The order of preference for the laboratory values are: (1) NGSP certified central laboratory values, (2) NGSP certified local laboratory values, and (3) non-NGSP certified local laboratory values. If a visit window includes a NGSP certified local laboratory value as well as a non-NGSP certified local laboratory value (either both being on- or post-treatment), then the NGSP certified value will be selected rather than the non-NGSP certified value. For study baseline, if none of these preference HbA1c values are available at Visit 2, then Screening data will be used.

7.3.1 Primary endpoint analyses

7.3.1.1 DINAMO

The primary endpoint of DINAMO™ is defined in [Section 5.1.1](#).

7.3.1.1.1 Analysis of the primary family of hypotheses

These confirmatory primary analyses will be performed using an effectiveness “wash-out” approach based on the mITT set with multiplicity adjustment for simultaneous testing of linagliptin and empagliflozin using the Hochberg-procedure. Patients will be assigned to the treatment they were randomised to at the initial randomisation, i.e. linagliptin 5 mg, pooled empagliflozin or placebo. HbA1c values measured after premature discontinuation of study drug or after rescue therapy was initiated will be included in the analyses. All available on- and off-treatment data up to the Week 26 time point will be included.

There will be different types of missing data to be considered for the imputation.

Table 7.3.1.1.1: 1 “Wash-out” approach – the missing data imputation method

Randomised treatment group: Placebo

Missing HbA1c data will be imputed for all scheduled visits up to Week 26, that includes Week 4, Week 12 and Week 26. Baseline will not be imputed.

Type of missing data	Data used for imputation	Method to use for	
		Non-monotone missing data	Monotone missing data
On- and off-treatment ⁴ data	Observed on- and off-treatment HbA1c data in the placebo group, including Baseline, Week 4, Week 12 and Week 26.	MCMC-MI ¹ (MAR ³)	SLR-MI ² (MAR ³)

Randomised treatment groups: linagliptin 5 mg and empagliflozin pooled.

Missing HbA1c data will be imputed for Week 26 only.

Type of missing data	Data used for imputation	Method
On-treatment data	Observed on-treatment HbA1c data in the respective treatment group, including Baseline and Week 26.	SLR-MI ² (MAR ³)
Off-treatment ⁴ data	Observed on- and off-treatment HbA1c data in the placebo group, including Baseline and Week 26.	SLR-MI ² (MNAR ⁵)

¹ Markov Chain Monte Carlo – Multiple imputation (MCMC-MI)

² Sequential linear regression – Multiple imputation (SLR-MI)

³ Missing at random (MAR)

⁴ Missing post-treatment data after permanent treatment discontinuation

⁵ Missing not at random (MNAR)

For the placebo group, missing HbA1c data, regardless on- or off-treatment, will be imputed for all scheduled visits up to Week 26.

The non-monotone missing data will be imputed using Markov Chain Monte Carlo (MCMC) simulation and standard techniques; multiple imputation (MI) will be performed on a data set including on- and off-treatment HbA1c data in the placebo group at baseline, Week 4, Week 12 and Week 26 with baseline HbA1c as a continuous covariate and age as a set of binary covariates corresponding to its class categorisation levels (age <15 years or age ≥ 15 to <18 years). 500 imputations will be performed to ensure adequate efficiency and stability of the estimation for missing data. This step will be referred to as “MCMC-MI”.

For the monotone missing data, a sequential linear regression MI approach will be used and referred to as ‘SLR-MI’. The MI will be performed on a data set including on- and off-treatment data and once per imputation from the previous step. This procedure will impute values for all missing time points both on- and off-treatment. The regression models will be fitted with baseline HbA1c as a continuous covariate and age as a binary covariate (age < 15 years and age ≥ 15 to <18 years). 500 imputations for the placebo group will be completed.

For the active treatment groups (linagliptin 5 mg and empagliflozin pooled, regardless of the dose level), missing HbA1c data will be imputed for Week 26 only separately for missing on-treatment data and missing off-treatment data.

To impute the missing on-treatment data, the MI will be performed on a data set including on-treatment HbA1c data in the respective treatment group at baseline and Week 26 only. The regression models will be fitted separately by active treatment group with baseline HbA1c as a continuous covariate and age as a binary covariate (age <15 years or age ≥ 15 to <18 years). 500 imputations for each active treatment group on-treatment data will be completed.

To impute the missing off-treatment data, the MI will be performed on a data set including patients with missing off-treatment HbA1c data at Week 26 in the active treatment groups and available on- and off-treatment HbA1c data in the placebo group at baseline and Week 26. The regression models will be fitted separately by active treatment group with baseline HbA1c as a continuous covariate and age as a binary covariate (age <15 years or age ≥ 15 to <18 years). 500 imputations for each active treatment group off-treatment data will be completed.

The effectiveness analyses will be performed on these imputed data sets plus the retrieved HbA1c data at Week 26 from the off-treatment patients, using an ANCOVA model with baseline HbA1c as a continuous model term, and with categorical terms for treatment and age. Rubin’s rules will be used to combine treatment estimates across the 500 completed imputations.

The implicit assumption underlying the imputations and analyses is that unobserved off-treatment patient measurements will lose any treatment effect immediately post-treatment discontinuation.

7.3.1.1.2 Analysis of the secondary family of hypotheses

If the “wash-out” approach analysis for both hypotheses in the primary family of hypotheses shows a statistically significant result, the secondary family of hypotheses will be tested as ordered hypotheses at the significance level $\alpha = 0.05$ (two-sided), i.e., the hypotheses $H'_{0,1}$ will be tested first and if this hypothesis can be rejected at the level $\alpha = 0.05$, the hypotheses $H'_{0,2}$ will be tested at the same level.

In using two sets of hypotheses families in a hierarchical order and using all hypotheses in the primary family as a gatekeeper for the secondary family, the experimentwise Type I error rate across both families is controlled by the significance level $\alpha = 0.05$.

These secondary family of hypotheses for the primary endpoint will be tested using the “wash-out” approach described in [Section 7.3.1.1](#) but the ANCOVA used for analysis of the completely imputed set will apply an “inverse probability weighting” approach based on the mITT set.

The ANCOVA model will utilise a weight variable having a value of 0 for the patients who are not in the hypothesis test of interest; a value of 2 for re-randomised patients who are in the hypothesis test of interest and a value of 1 otherwise. The model terms will include baseline HbA1c as a continuous variable, and treatment and age as categorical variables. Rubin’s rules will be used to combine treatment estimates across the 500 imputations.

Patients will be assigned to the treatment they were randomised to at the initial randomisation together with the treatment allocation at Week 14 randomisation. HbA1c values measured after premature discontinuation of study drug or after rescue therapy was initiated will be included in the analyses. All data up to the Week 26 time point will be included.

The treatment comparisons for $H'_{0,1}$ and $H'_{0,2}$ according to [Section 7.2.2](#) are as follows:

For $H'_{0,1}$, this is a contrast between patients who started empagliflozin 10 mg and either having a dose increase in patients who were non-responder at Week 12, or who were responders at Week 12 and continue with empagliflozin 10 mg, and placebo.

For $H'_{0,2}$, this is a contrast between patients who started empagliflozin 10 mg and either were responders or were non-responders at Week 12 and continue with empagliflozin 10 mg, and placebo.

7.3.1.2 DINAMO Mono

The primary endpoint of DINAMO™ Mono is defined in [Section 5.1.1](#).

The primary analysis will be a comparison of the treatment failure rates of linagliptin 5 mg, pooled empagliflozin and placebo. The risk difference of active treatments versus placebo will be determined and assessed by an exact 2-sided 90% confidence interval based on the method of Chan and Zhang [[R15-1346](#)]. Patients will be assigned to the treatment they were

randomised to at the initial randomisation. Non-completers who prematurely discontinue intake of study drug will be considered treatment failures.

7.3.2 Secondary endpoint analyses

7.3.2.1 DINAMO

Secondary endpoints of DINAMOTM are defined in [Section 5.1.2](#).

For the secondary endpoints, the patients initially randomised to empagliflozin (empagliflozin 10 mg and empagliflozin 25 mg pooled) and linagliptin 5 mg will be compared versus placebo. Analyses will be performed on the mITT set and will apply two approaches.

The *first approach* will use all observed data including data after premature discontinuation of study drug or post rescue medication data up to Week 26.

The change in FPG from baseline to the end of 26 weeks will be analysed using an ANCOVA model. The statistical model will be:

FPG change from baseline to the end of 26 weeks =
overall mean + treatment + baseline FPG + age + random error

Treatment is a fixed classification effect. Baseline FPG is a linear covariate and age a categorical covariate. The random error is assumed to be normally distributed with mean 0 and unknown variance σ^2 .

The other continuous secondary endpoints will be analysed based on a restricted maximum likelihood (REML) approach using a mixed model for repeated measurements (MMRM). The analyses will include the fixed categorical effects of treatment, visit, and treatment by visit interaction, as well as the categorical covariate age and the continuous, fixed covariates of baseline of the response variable and baseline of the response variable by visit interaction. The covariate visit will be treated as the repeated measure with an unstructured covariance structure used to model the within-patient measurements.

The Kenward-Roger approximation will be used to estimate denominator degrees of freedom and adjust standard errors. The residuals are assumed to have a multivariate normal distribution with zero means and covariance matrix as specified above.

The *second approach* will include only on-treatment values measured prior to the start of any rescue medication up to Week 26.

The change in FPG from baseline to the end of 26 weeks will be analysed using the ANCOVA model, which is described in the first approach, but using the second approach data.

For the other continuous secondary endpoints analyses, values measured after rescue therapy was initiated or after premature discontinuation of study drug will be set to missing. The missing data will not be imputed. The MMRM model will handle missing data based on a likelihood method under the "missing at random" assumption.

The proportion of patients who achieve HbA1c < 7.0% and < 6.5% at the end of 26 weeks will be determined per treatment group and the risk difference of active treatments versus placebo will be determined and assessed by an exact 2-sided 95% confidence interval.

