The primary endpoint of the final analysis was the change from baseline in HbA1c (%) after 12 weeks of treatment. Because of the early termination of the study, the trial had limited statistical power. After 12 weeks of treatment, the adjusted mean treatment difference between linagliptin 5 mg and placebo was -0.63 (95% CI: $-1.50, 0.23$; $p = 0.1447$). The adjusted mean treatment difference between linagliptin 1 mg and placebo was -0.48 (95% CI: $-1.47, 0.51$; $p = 0.3295$). As expected because of the limited power of the trial, a statistically significant difference to placebo could be demonstrated neither for the linagliptin 1 mg dose nor for the linagliptin 5 mg dose. The reduction of -0.63 with linagliptin 5 mg is considered clinically meaningful. The results were in accordance with data from adult patients after 12 weeks of treatment with linagliptin 5 mg. The median change from baseline in HbA1c (%) was $+0.50$ in the placebo group, -0.05 in the linagliptin 1 mg group, and -0.30 in the linagliptin 5 mg group. The difference to placebo was -0.80 in the linagliptin 5 mg group compared with -0.55 in the linagliptin 1 mg group. The results were consistent with data from adult patients after 12 weeks of treatment with linagliptin 5 mg. In the linagliptin 5 mg group, a reduction in HbA1c compared with baseline was seen over the entire randomised treatment period. In contrast, HbA1c had returned almost to baseline in the linagliptin 1 mg group and had increased beyond baseline HbA1c in the placebo group at Week 12. The percentage of patients with a relative efficacy response (HbA1c lowering by at least 0.5%) was greater in the linagliptin 5 mg group (30.8%) than in the linagliptin 1 mg group (20.0%) or placebo group (14.3%). Furthermore, the proportion of patients who had a baseline HbA1c $\geq 7\%$ and reached target HbA1c $< 7\%$ (absolute efficacy response) was greater with linagliptin 5 mg (36.4%) than with placebo (18.2%), whereas it was 10.0% with linagliptin 1 mg. A target HbA1c $< 7\%$ is more difficult to achieve for patients with a higher baseline HbA1c value than for patients with a lower baseline HbA1c value.

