3.3.2 Inclusion criteria

1. Patients aged 10 to 17 years (inclusive) at the time of randomisation (Visit 2)
2. Male and female patients
3. Women of childbearing potential (WOCBP)¹ must be ready and able to use highly effective methods of birth control per ICH M3 (R2) that result in a low failure rate of less than 1% per year when used consistently and correctly. A list of contraception methods meeting these criteria is provided in the patient's legal representative information sheet as well as in [Section 4.2.2.3](#).
4. Signed and dated written informed consent provided by the patient's parent(s) (or legal guardian) and patient's assent in accordance with ICH-GCP and local legislation prior to admission to the trial (informed assent will be sought according to the patient's age, level of maturity, competence and capacity)
5. Documented diagnosis of T2DM at Visit 1A:
 - a. DINAMO™: Documented diagnosis of T2DM for at least 8 weeks at Visit 1A
 - b. DINAMO™ Mono: Confirmation of T2DM at Visit 1A

¹ A woman is considered of childbearing potential (WOCBP), i.e. fertile, following menarche and until becoming postmenopausal unless permanently sterile.

Permanent sterilisation methods include hysterectomy, bilateral salpingectomy and bilateral oophorectomy.

Tubal ligation is NOT a method of permanent sterilisation.

A postmenopausal state is defined as no menses for 12 months without an alternative medical cause.

6. Insufficient glycaemic control as measured by the central laboratory at Visit 1A:
 - a. DINAMO™: HbA1c $\geq 6.5\%$ and $\leq 10.5\%$
 - b. DINAMO™ Mono: HbA1c $\geq 6.5\%$ and $\leq 9.0\%$

 7. a. DINAMO™: Patients treated with
 - diet and exercise plus metformin at least 1000 mg/day (or up to a maximal tolerated dose) at a stable dose for 8 weeks prior to Visit 2 or not tolerating metformin (defined as patients who were on metformin treatment for at least 1 week and had to discontinue metformin due to metformin-related side effects as assessed by the investigator)AND/OR
 - diet and exercise plus stable basal or MDI insulin therapy, defined as a weekly average variation of the basal insulin dose ≤ 0.1 IU/kg over 8 weeks prior to Visit 2
 - b. DINAMO™ Mono: Drug-naïve patients or patients not on active treatment (including discontinuation of metformin due to intolerance [or previous discontinuation for other reasons] and/or discontinuation of insulin [insulin use must be 8 weeks or less] at investigator's discretion) prior to or at Visit 1A)

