7.6 RANDOMISATION

At visit 2, patients will be randomised in blocks to double-blind treatment. Approximately equal numbers of patients will be randomised to each treatment group. The randomisation will be stratified by age (<15 years; ≥15 to <18 years). It will be monitored and capped so that at least 30% but no more than 70% of the randomised patients are < 15 years. For DINAMO™ only, the randomisation system will also include caps for gender so that at least 30% but no more than 70% of the randomised patients are girls.

At visit 4B, patients from the empagliflozin 10 mg arm who do not achieve an HbA1c < 7.0% at Week 12 will be re-randomised in blocks to double-blind treatment with either empagliflozin 10 mg or empagliflozin 25 mg. This re-randomisation will be stratified by age at baseline (< 15 years; ≥ 15 to <18 years). Practically, an IRT call will be performed for all patients to maintain double-blind conditions but only patients on empagliflozin 10 mg with HbA1c ≥ 7.0% at Week 12 may get new trial treatment re-assigned.

At visit 5, patients from the placebo arm will be re-randomised in blocks to double-blind treatment. Approximately equal numbers of patients will be re-randomised to empagliflozin 10 mg, empagliflozin 25 mg, or linagliptin 5 mg. The re-randomisation will be stratified by age at baseline (<15 years; ≥15 to <18 years). Practically, an IRT call will be performed for all patients to maintain double-blind conditions but only patients on placebo may get new trial treatment re-assigned.

BI will arrange for the randomisation and the packaging and labelling of trial medication. The randomisation list will be generated using a validated system, which involves a pseudo-random number generator so that the resulting treatment will be both reproducible and non-predictable. The block size will be documented in the Clinical Trial Report (CTR). Access to the codes will be controlled and documented. The method of assigning patients to treatment groups is described in [Section 4.1.3](#).

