Table 6.3: 1 Patient sets analysed and treatment groupings (continued)

Class of endpoint	Patient sets					
	SCR	TS	TSactive	RS	mITT	PPS
Secondary efficacy endpoints						
Change in FPG [mg/dl] from baseline - ANCOVA					OC-AD-BOCF; OC (TG1)	
Change in body weight [kg] / SBP [mmHg] / DBP [mmHg] from baseline – MMRM					OC-AD; OC (TG1)	
Proportion of patients who achieve HbA1c goals < 6.5% and < 7.0%. Exact CI					NCF; OC (TG1)	

Table 6.3: 1 Patient sets analysed and treatment groupings (continued)

Class of endpoint	Patient sets					
	SCR	TS	TSactive	RS	mITT	PPS
Further safety endpoints						
Shift tables for the Tanner staging score from baseline		OC-AD (TG1, TG5)				
Descriptive statistics over time for growth velocity		OC-AD (TG1, TG5)				
Safety evaluation						
Overall summary of AEs		TG1, TG5, TG4	TG6			
Freq. of patients with the following AEs by treatment, SOC and PT 
 
• AEs
 
• AEs by worst intensity
 
• Drug-related AEs
 
• AEs leading to treatment discontinuation
 
• SAEs
 
• Other significant adverse events
 
• AESIs(except DKA and lower limb amputation)
 
		TG1, TG5, TG4	TG6			
Incidence rate of patients with AEs by treatment, SOC and PT		TG1, TG5				
List of patients with AESIs/other significant AE 
 
• DKA
 
• Events involving lower limb amputation
 
• Bone fracture
 
		TS				
Freq. of patients with other specific AE by treatment, SOC and PT: 
 
• Hypoglycaemic AE
 
• UTI (also investigator assessment, serious and leading to treatment discontinuation)
 
• Genital infection (also investigator assessment, serious and leading to treatment discontinuation)
 
• Acute pyelonephritis or urosepsis
 
• Volume depletion
 
• Ketone measurements
 
		TG1, TG4	TG6			

Table 6.3: 1 Patient sets analysed and treatment groupings (continued)

Class of endpoint	Patient sets					
	SCR	TS	TSactive	RS	mITT	PPS
Freq. of patients with other specific AE by treatment, SOC and PT: 
 
• Arthralgia
 
• Pemphigoid in bullous conditions)
 
		TG1	TG6			

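### DINAMO, HbA1c < 7.0% at Week 26: the visible plan gives only an unadjusted risk difference; a supportive estimate adjusted for baseline HbA1c would be a cheap, modest gain in precision

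*Protocol*

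**What the plan says.** Protocol 7.3.2.1 plans, for the two HbA1c target endpoints in DINAMO, the proportion per treatment group, and then "the risk difference of active treatments versus placebo will be determined and assessed by an exact 2-sided 95% confidence interval". SAP 7.5.2.1 repeats this twice on the mITT set: once with non-completers counted as failures (NCF) and once on observed cases (OC). SAP Table 6.3: 1 lists the method as "Proportion of patients who achieve HbA1c goals < 6.5% and < 7.0%. Exact CI". No covariate, stratum or model is named in these places.

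Four other statements bear on the choice:

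- Protocol 7.3: the mITT set "will include all randomised patients who are treated with at least one dose of study medication and have a baseline HbA1c measurement". Baseline HbA1c is therefore complete by definition.
- Protocol 1.2.2, on the earlier paediatric linagliptin trial: an HbA1c target below 7% "is more difficult to achieve for patients with a higher baseline HbA1c value than for patients with a lower baseline HbA1c value".
- Protocol 7.3.1.1.1: the continuous HbA1c change is analysed "using an ANCOVA model with baseline HbA1c as a continuous model term, and with categorical terms for treatment and age".
- Protocol 7.6: "The randomisation will be stratified by age".

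Fasting glucose, body weight and blood pressure are also adjusted for their own baseline and for age (Protocol 7.3.2.1, SAP 7.5.2.1). In the visible text, the two HbA1c targets are the only DINAMO primary or secondary efficacy endpoints without baseline adjustment.

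**The concern.** Baseline HbA1c varies widely at entry (6.5% to 10.5% at screening). A patient who starts near 7% has a very different chance of ending below 7% from one who starts near 10%. An unadjusted comparison leaves that variation in the standard error. With about 50 patients per arm the interval is wide in any case, and the sample was kept small to limit the exposure of children (Protocol 7.7.1). It is reasonable to get what precision one can from a value already in the database.

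Only the width of a descriptive interval is at stake. The endpoint is outside both families of hypotheses, and SAP 5.2.1 states that there are no key secondary endpoints.

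**Working it through.** **Inputs from the documents**

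- 50 patients per group, effect -0.55, covariate-adjusted SD 0.8, 0.9 or 1.0 (Protocol 7.7.1).
- The 6.5-10.5% limit is applied as "Insufficient glycaemic control as measured by the central laboratory at Visit 1A", whereas study baseline is normally the Visit 2 value: "For study baseline, if none of these preference HbA1c values are available at Visit 2, then Screening data will be used". The limit was therefore imposed on the Visit 1A value only.

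**Assumptions not in the documents**

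- True baseline mean 7.5-8.5, SD 0.8-1.2; within-patient SD 0.2 or 0.4 between Visits 1A and 2.
- Slope of Week 26 HbA1c on baseline 0.5-1.0.
- 0% or 20% NCF failures, unrelated to baseline; no age effect.

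**Reproducing the plan's figures.** The plan states no precision for the target endpoints. Its power table for HbA1c change (Table 7.7.1: 2) reproduces with a two-sided t-test: 77.7, 85.7, 92.6, 68.2, 78.1 and 87.5%, against the stated 77, 85, 92, 68, 78 and 87%.

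**Width of the unadjusted interval.** The only paediatric rates for < 7% in the documents are 36.4% on linagliptin 5 mg and 18.2% on placebo (Protocol 1.2.2; 12 weeks, baseline at least 7%). Large-sample width = 2 x 1.96 x sqrt[(0.364 x 0.636 + 0.182 x 0.818)/50] = 34.2 percentage points.

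**Method.** Two-arm trials were simulated. The crude risk difference was compared with a standardised one: fit a logistic model, predict every patient under each treatment, average, and subtract. Saving = 1 - (empirical variance adjusted / empirical variance crude).

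**One case in full** (mean 8.0, observed baseline SD 0.93, residual SD 0.9, 10% NCF failures, adjusted for baseline and age, 2,500 trials):

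- Slope 1.0: risk difference 0.124 crude, 0.123 adjusted; SE 0.0829 and 0.0735. Ratio (0.0735/0.0829)^2 = 0.786, so 50 per arm acts like 50/0.786 = 64.
- Slope 0.7: risk difference 0.135 in both; variance ratio 0.848, so 50/0.848 = 59 per arm.

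**Range at < 7.0%**

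| Setting | Variance saving |
|---|---|
| 144 scenarios, slope 0.7-1.0, residual SD 0.8-1.0, baseline and age | 4.5-37.4%, median 16.4% |
| Same scenarios, baseline only | 6.2-38.1%, median 17.5% |
| 72 scenarios, slope 0.5, residual SD 0.8-1.0 | 0.5-13.7% |
| Residual SD 1.15, slope 0.5 / 0.7 / 1.0 | 1.5-4% / 7-10% / 15-20% |
| Separate runs, baseline only, residual SD 0.9 | 7-31% |
| Separate runs, baseline only, residual SD 1.15 | 7-23% |

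The value 1.15 comes from the paediatric linagliptin trial (95% CI -1.50 to 0.23). Half-width 0.865, divided by a t multiplier of about 2.03, gives SE 0.426. Dividing by sqrt(1/14 + 1/15) = 0.372 gives an SD of about 1.15. With 13 and 14 analysed, as the response percentages suggest (4/13 = 30.8%, 2/14 = 14.3%), it is about 1.11.

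**Conversion to width.** Width saving = 1 - sqrt(1 - variance saving). For 7% this is 1 - sqrt(0.93) = 3.6%; for 17% it is 1 - sqrt(0.83) = 8.9%. Applied to 34.2 points, the width becomes about 33 or 31.

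**At < 6.5%.** The same 144 scenarios, with baseline and age, run from a 9% variance loss to a 29% saving. With slope 0.5 they run from a 19% loss to a 9% saving. Losses arise where successes are few.

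**Age.** The age term reduced the saving by 0.4-2.4 points at < 7.0%.

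**Coverage.** The adjusted 95% interval covered about 93-95% at < 7.0%. In the slope 1.0 case above, the mean interval width of 0.279 is below 2 x 1.96 x 0.0735 = 0.288, so the influence-function SE is slightly too small. The sizes here therefore rest on empirical variances.

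**The case against.** The strongest reply is that this is a preference. The unadjusted difference is unbiased, the exact interval is valid, and an exact method is a defensible choice at 50 per arm. Efficient inference on HbA1c already comes from the baseline-adjusted ANCOVA. All of that stands, and it is why this is only an optional improvement.

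Second, the size depends on inputs that the documents do not give. The SDs of 0.8-1.0 come from adult trials. At the SD of about 1.15 implied by the paediatric trial, with a slope of 0.5, the saving falls to 1.5-4%. This stands and is included in the range. It shrinks the gain without removing it.

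Third, the comparison is between large-sample intervals, whereas the plan uses an exact one. For 20/50 against 10/50, the Chan-Zhang interval (the method named for DINAMO Mono) is +1.5 to +37.5 points and the large-sample one +2.5 to +37.5. Any extra narrowing against the exact interval would be bought by giving up guaranteed coverage. No systematic comparison with the exact width was made, and none is claimed.

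Fourth, absence cannot be shown. A reader might infer that the SAP contains no adjusted analysis of this target. The documents do not support that: the SAP history table shows that target-proportion wording also sits in SAP 5.3.1, which is withheld. SAP 7.8.2.4 also mentions eGFR in connection with covariates for efficacy modelling, yet no visible efficacy model contains eGFR.

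**Conclusion.** The point holds for < 7.0% as a cheap, optional improvement. In the visible text this endpoint has only an unadjusted analysis, and a complete covariate that the protocol links to the target is left unused. Adjusting for baseline HbA1c would lower the variance by roughly 1-37% (38% at the very top with baseline alone), typically 7-17%, or about 4-9% in interval width on a like-for-like large-sample basis. This rests on an assumed slope of 0.5-1.0, residual SD of 0.8-1.15, and NCF failures unrelated to baseline. The estimate itself hardly moves.

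Two stronger readings are tempting and are not supported:

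- That the planned analysis is biased or wrong, or that a confirmatory conclusion is at risk. Randomisation makes the crude difference unbiased, and the endpoint is outside the confirmatory families.
- That the same gain is available at < 6.5%. There the gain is smaller and can turn into a loss, and the protocol's remark about baseline concerns the < 7% target.

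**What to change.** In SAP 7.5.2.1:

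1. Keep the exact unadjusted interval as the main analysis for both targets.
2. For < 7.0% on the mITT (NCF) set only, add one supportive analysis: the standardised risk difference against placebo with a 95% CI, from a logistic model with treatment and baseline HbA1c. The age stratum may be added for consistency with the randomisation, but it brings no precision.
3. Name the standard error (robust or bootstrap), name penalised likelihood as the fallback if the model separates, and say whether the model uses all three groups or each pair. The simulations were pairwise.
4. Report the result whatever the number of successes. Do not use a display rule that depends on the outcome.

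The wording needs to be fixed before unblinding; otherwise the result is post hoc. The cost is a few lines of SAP text, one model and two extra intervals (linagliptin and pooled empagliflozin, each against placebo), with no new data. The downside is that the interval is a large-sample one, with coverage of about 93-95%, so it can only support the exact interval. If a withheld section already contains an adjusted analysis, no change is needed.
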